Randomization table was pre-generated using SAS. Randomization occurs using blocked, stratified randomization by operation. Randomization table was pre-generated onto spreadsheets, with rows hidden (in Excel). Each randomized patient will receive the next available row (unhidden by the coordinator at 14 days post-surgery for randomization as needed).

The PI will be blind to the patient's randomization status until completion of analyses. Due to the limitations of REDCap's randomization module, the research coordinator cannot be blinded to the randomization status of the participant.

Enhanced Usual Care (EUC)

Participants will receive phone calls matching the duration and frequency of MI+GOW calls. [name], NP will contact participants via phone to review one topic per call in this sequence: 1) standardized instructions on taking opioid medications after surgery, 2) avoiding medication mistakes, 3) alternative methods for pain management after orthopedic surgery, 4) understanding complementary and alternative medicine, 5) safe opioid use, 6) local mental health resources (including a suicide prevention hotline), 7) prescription drug abuse. She will briefly review patient education brochures in a didactic style without a tailored discussion. She will remind participants to complete REDCap assessments.

Intervention

The experimental intervention arm is Motivational Interviewing and Guided Opioid Weaning (MI+GOW). A pain medicine nurse practitioner ([name], NP) will administer MI+GOW. See table below for MI Components. The GOW protocol will be a 25% total daily opioid dose reduction every 7 days with opioid discontinuation 7 days after reaching 1 opioid pill per day. During phone sessions, patients will be monitored for worsening pain and opioid withdrawal through administration of the NRS and SOWS with the protocol specified in the "Guided Opioid Weaning" table below. Participants will be reminded that they can always use less opioids than recommended. Non-adherence is opioid use greater than previously recommended via the last phone call. During the randomization call, the first MI appointment should be scheduled by referring to [name]'s schedule.

Table MI Components

Principles	Strategies	Information Recorded by Interventionist	Information and Advice Offered in an MI-consistent manner (Elicit patient's knowledge, Provide advice, Elicit feedback)
------------	------------	---	---

MAP-Pain Standard Operating Procedures

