An additional 10% of data will be randomly verified by study staff prior to data analysis. Verification will occur via visual inspection. Discrepancies will be noted, original source data checked, and the correct value entered. All verified data will be noted with the reviewer's initials and date. Corrections will be noted with the date, initials, and reason for correction. Consistent errors will prompt a more comprehensive review of the data at the PI's discretion.

MAP-Pain Standard Operating Procedures

Primary Efficacy Outcome-Observation Arm

Time to opioid cessation, defined as the first of 2 consecutive reports of opioid cessation on the modified BPI.

Secondary Efficacy Outcomes-Observation Arm

1. Opioid misuse (This will be defined as a score of 9 or higher on the Current Opioid Misuse Measure).
2. Time to pain cessation (This will be defined as the first of five consecutive days of 0 average pain).
3. Time to recovery (First report of patient indicated "Yes" to having recovered from surgery).

Primary Efficacy Outcome-Intervention Arm

Time to opioid cessation, defined as 1st of 2 consecutive reports of return to baseline opioid dose or lower.

Secondary Efficacy Outcomes-Intervention Arm

1. Opioid misuse (This will be defined as a score of 9 or higher on the Current Opioid Misuse Measure).
2. Time to complete opioid cessation, defined as the first of 2 consecutive reports of opioid cessation on the modified BPI.
3. Time to pain cessation (This will be defined as the first of five consecutive days of 0 average pain).
4. Time to recovery (First report of patient indicated "Yes" to having recovered from surgery).
5. Treatment engagement is defined as participation in >50% of phone sessions.
6. Treatment initiation is defined as participation in at least 1 phone session.

Methods for handling missing data and non-adherence to protocol:

Subjects dropping out will be censored at the last known data point. Competing events such as a second surgery will be reasons for censoring at the time of the competing event. Missing data will not be imputed.

Modifications History

Last Updated 10/15/2020 by [name], CRC.

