Study Title:

Motivational Interviewing and Guided Opioid Tapering Support to Promote Postoperative Opioid Cessation

NCT03659734

Document Date: 2/26/2019

Analytic Plan: Results of Cox and logistic regression analyses will be reported with and without stratification by gender. The intention-to-treat (ITT) analysis will include all patients with at least one set of follow-up data after randomization. We will examine the distribution of baseline covariates amongst groups to establish adequacy of randomization. We will use Kaplan Meier analysis and the log-rank test of significance to compare the groups at a two-sided a level=0.05, to identify a difference in time to opioid cessation. We will use Cox regression to adjust for potential confounders only if randomization is inadequate, and for surgery type. (Adequate randomization should adjust for confounding. In the event that the baseline covariate distribution amongst the groups are unbalanced, these specific covariates will be tested as potential confounders.) We will evaluate the effect of treatment group on time to opioid cessation. For sensitivity analyses, we will compare models from manual and automated selection techniques through AIC values. We will test for non-violation of the proportional hazards assumption and linearity assumptions of continuous predictors. Secondary outcomes include time to complete opioid cessation.

In a similar ITT analysis, we will compare the proportion of postoperative opioid misuse between groups, using the chi-square test. We will use logistic regression to characterize the effect of group on postoperative opioid misuse, with adjustment for confounders (only if randomization is inadequate) and surgery type. Sensitivity analyses will similarly compare -2 Log L scores of models. We will test linearity assumptions of significant predictors.

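### The SAP does not say whether the unstratified log-rank or the surgery-adjusted Cox model decides the primary comparison, and it leaves most covariate adjustment to an undefined imbalance check

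*SAP*

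**What the plan says.** **Design.** Protocol, Blinding and Randomization Methodology: "Randomization occurs using blocked, stratified randomization by operation". The Randomization section shows two levels, hip and knee replacement.

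**Primary comparison.** SAP, Analytic Plan: "We will use Kaplan Meier analysis and the log-rank test of significance to compare the groups", at a two-sided level of 0.05. This is the only alpha in the SAP, and no strata are named. The Cox model follows: "We will use Cox regression to adjust for potential confounders only if randomization is inadequate, and for surgery type". Surgery type is therefore always in the Cox model. Nothing says which of the two results decides.

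**Other covariates.** The trigger is: "We will examine the distribution of baseline covariates amongst groups to establish adequacy of randomization". If some are unbalanced, "these specific covariates will be tested as potential confounders". There is no list, measure, threshold or rule for keeping a covariate once tested. Two other routes exist in the same paragraph: Cox and logistic results are reported with and without stratification by gender, and sensitivity analyses compare models from manual and automated selection.

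**Misuse.** "we will compare the proportion of postoperative opioid misuse between groups, using the chi-square test", followed by logistic regression "with adjustment for confounders (only if randomization is inadequate) and surgery type".

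**Endpoint and available data.** Protocol, Primary Efficacy Outcome-Intervention Arm: "Time to opioid cessation, defined as 1st of 2 consecutive reports of return to baseline opioid dose or lower". Baseline opioid use (BPOQ) and baseline misuse score (COMM) are both in the Baseline Questionnaire Packet.

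The protocol's contents page also lists sections on the data analysis plan and on power. Neither is in the supplied text.

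**The concern.** A factor used to stratify randomisation would normally appear in the decisive test. Here it appears in the models but not, as written, in the test that carries the alpha. If the two results fall on opposite sides of 0.05, the SAP gives no rule for which to report as the trial's answer.

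The imbalance rule is a separate weakness. In a properly randomised trial, imbalance is mainly chance, so a trigger based on it says little about whether a covariate predicts outcome. It leaves the adjusted model to be settled after the data are seen by arm, and it forgoes precision whenever a prognostic covariate happens to be balanced. Baseline opioid use is the clearest case: it must be known to score the primary endpoint, yet in the main analysis it is adjusted for only if it looks unbalanced.

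**Working it through.** **Inputs.** From the documents: 220 in the intervention arm with 10% censoring (Protocol, Study Overview), taken here as 220 randomised; two operation strata; two-sided 0.05. Assumed, because the supplied text does not give them: 1:1 allocation, blocks of 4, strata of 110 each, exponential times, random censoring, and all effect sizes.

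**The plan's own figure.** At most 220 × 0.90 = 198 events, if every uncensored participant reaches the endpoint. Without a stated hazard ratio (HR) or power, 220 cannot be reproduced. For orientation, the HR detectable with 80% power is exp[2(1.960 + 0.842)/√198] = exp(5.604/14.07) = 1.49.

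**Step 1. Strata and the log-rank.** Power (%) at treatment HR 1.49, with 10,000 simulated trials per row (Monte Carlo SE 0.4 points):

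| Operation HR | Log-rank | Stratified log-rank | Cox + surgery type | Log-rank and Cox disagree |
|---|---|---|---|---|
| 1.25 | 78.1 | 78.3 | 78.6 | 2.3 |
| 1.5 | 77.0 | 78.4 | 78.9 | 4.7 |
| 2.0 | 73.4 | 78.6 | 79.2 | 8.3 |

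The loss from not stratifying is 0.2, 1.4 and 5.2 points. A second simulation (treatment HR 1.5, 4,000 trials per cell) gave 80.5 − 79.3 = 1.2 points at operation HR 1.5, 81.5 − 75.7 = 5.8 at 2.0, and about 13 at 3. The Cox column shows that the planned model already recovers the loss.

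Under no treatment effect, each test in the first set rejected in 4.6–5.5% of trials. In the second set the unstratified log-rank fell to 3.2% at operation HR 3, which is conservative. At least one of log-rank and Cox rejected in 5.7–6.3%.

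**Step 2. What the trigger catches.** With p<0.05 as a stand-in for the missing threshold, one given covariate is flagged in about 5% of trials. At least one of k independent covariates is flagged with probability 1 − 0.95^k: 40% for k = 10 and 46% for k = 12. For 12 covariates with pairwise correlation 0.3 or 0.5, simulation gives 39% or 32%. The rule would fire often, but seldom on the covariate that matters.

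**Step 3. Fixed covariate.** Power (%) with the log-rank tuned to about 80%: Cox + surgery type, then Cox stratified by operation plus one covariate:

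| Log-hazard SD | Operation HR 1.25 | Operation HR 1.5 |
|---|---|---|
| 0 | 81.4 → 80.5 (−0.9) | 82.5 → 81.6 (−0.9) |
| 0.2 | 80.6 → 82.1 (+1.5) | 81.6 → 83.0 (+1.4) |
| 0.3 | 80.6 → 84.4 (+3.8) | 81.4 → 85.2 (+3.8) |
| 0.5 | 80.1 → 90.3 (+10.2) | 80.8 → 90.3 (+9.5) |

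This table changes two things at once: adjusting becomes stratifying, and a covariate is added. The second simulation isolates the covariate (Cox with surgery type throughout, treatment HR 1.5, operation HR 1.5, 2,500 trials per cell). At a covariate HR of 1.5 per SD (log-hazard 0.41), power is 72.6% without the covariate, 73.4% if it enters only when unbalanced at p<0.05, and 81.0% if it always enters. At 2.0 per SD the figures are 58.4%, 59.5% and 81.1%. Triggered adjustment recovers only about 1 point.

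**Step 4. What those SDs require.** If baseline opioid use is coded user or non-user with prevalence p (assumed), the HR needed is exp[SD/√(p(1−p))]. At p = 0.5 this is exp(0.2/0.5) = 1.49, exp(0.3/0.5) = 1.82 and exp(0.5/0.5) = 2.72. At p = 0.25 the divisor is 0.433, and the HRs are 1.59, 2.00 and 3.17.

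**Step 5. Misuse.** Strata: with n = 198, an assumed risk near 25% and a treatment odds ratio of 0.4, chi-square power against Cochran-Mantel-Haenszel is 68.4 and 68.2% at operation odds ratio 1, 68.3 and 68.6% at 2, and 67.1 and 69.1% at 4. The largest gap is 2.0 points. Baseline COMM: with chi-square power near 80% (25% against 10.7%, or 15% against 4.3%; n = 220; likelihood-ratio test), adding it to the planned logistic model changes power by −0.3 to 0 points at correlation 0 between baseline and follow-up, by +0.9 to +1.6 at 0.3, and by +4.1 to +5.3 at 0.5.

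**The case against.** Much of the design is already respected. Surgery type is in both models unconditionally, and the planned Cox model does slightly better than a stratified log-rank in every row of Step 1. A short SAP that is silent on strata has not said that strata will be ignored. Only one test carries an alpha, so it can be read as the main one, and an analysis section that was not supplied may say so. The larger gains depend on prognostic strengths that no document supports: needing baseline dose to score the endpoint does not show that it predicts time to the endpoint. The p<0.05 trigger is a stand-in, since the SAP speaks only of examining distributions. The analysed set also requires some follow-up after randomisation, so imbalance in it need not be pure chance.

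All of this stands, and it limits the size of the point. It does not supply a covariate list, a threshold, an inclusion rule or a rule for conflicting results.

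Three stronger readings are tempting and are not supported:
- That covariates enter only through the imbalance check. Surgery type, gender-stratified reporting and the sensitivity model selection are other routes.
- That an unstratified test inflates type I error. It is nominal or conservative.
- That the plain chi-square for misuse does real damage by omitting operation. The cost is at most about 2 points, even at an operation odds ratio of 4.

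**Conclusion.** The point holds as a matter of efficiency and pre-specification, not validity. The text leaves two things open: which analysis decides the primary comparison, and which covariates the adjusted model contains.

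The strata part is small. It is about 0 to 2 points of power at operation HR 1.25–1.5 and 5 to 6 at 2.0, and it is recovered if the planned Cox model is the decisive analysis. The two planned tests would disagree on significance in roughly 2 to 8% of trials over that range. The covariate part is potentially larger: about 1.5, 4 or 10 points at log-hazard SD 0.2, 0.3 or 0.5, with about 1 point lost if the covariate has no prognostic value. An SD of 0.5 would need a strong effect of baseline opioid use (HR about 2.7 to 3.2 if binary), so the lower figures are the safer guide.

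Every figure rests on assumed effect sizes, equal strata, 1:1 allocation and blocks of 4. The ranking of the tests may be settled in the analysis section that was not supplied.

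**What to change.** Name one decisive primary analysis: a Cox model stratified by, or adjusted for, operation and including baseline opioid use from the BPOQ. Fix the coding of that covariate before unblinding and use it whatever the balance. State that the resulting hazard ratio is conditional on the covariate. Keep the Kaplan-Meier curves and the unstratified log-rank as supportive, and delete the imbalance trigger from both models.

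For misuse, lead with the logistic model already planned, with surgery type and baseline COMM, and keep the chi-square as supportive. Specify a likelihood-ratio test for treatment: at 15% against 4.3% misuse, a Wald test of the logistic model with surgery type had 76.4–77.0% power against 79.7–80.3% for the chi-square.

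The cost is SAP text and no new data. Transfer to follow-up requires completed pre-surgical assessments, so few baseline values should be missing. Because the protocol rules out imputation, one line should still say how a missing baseline value is handled. The principal investigator is to stay blind until analyses are complete, so the change can be made credibly before unblinding. The downside is about 1 point of power if the covariate proves not to be prognostic. If the unsupplied analysis section already names the decisive test, only the covariate part is needed.
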